An illusion of the virtual limb is crafted by mirroring the patient's symmetric anatomical limb in the captured data using various computer vision and graphics techniques. The major challenges in developing the [name] framework are: a) capturing the live 3D models of the human, b) generating the 3D model for the phantom limb in the real-time, c) generating corresponding movement in the real-time, and d) rendering the 3D model of the person along with phantom limb for the immersive and interactive experience.

Also, to make the therapy sessions more engaging, fun and non-monotonous, it is also required to design an attractive virtual environment and game with the engaging task. Figure 1 shows the virtual environment developed for [name] framework. The quantitative and qualitative evaluation of the [name] framework is performed by a group of able-bodied participants and Subject-Matter Experts (SME). The results indicate the effectiveness and usefulness of the [name] framework. Given the encouraging results of existing studies to determine the effectiveness of a classic mirror-box therapy, it also becomes crucial to evaluate the efficacy of virtual mirror box therapy using [name] framework in a similar manner.

Feasibility and Functional Outcomes of a Novel Mixed Reality based system to manage phantom pain for patients with lower limb amputation.

3

[figure not shown]

Figure 1-a: Real scene with healthy user keeping her right hand behind (to simulate amputation) Figure 1-b: Virtual scene with phantom limb.

2- Purpose

The primary goals of this pilot research project are a) to design and develop a mixed reality based system for managing phantom pain and b) to evaluate the feasibility and preliminary functional outcomes of this system in a sample of patients with lower limb amputation. Findings from this pilot study will serve as preliminary data to inform regarding a fully powered clinical trial to determine the effectiveness and practical implementation of these findings in real-world settings.

Aim1: Design and develop a feasible mixed reality-based system to manage phantom pain in patients with lower limb amputation qualifying for on-going mirror therapy.

Hypothesis 1: We hypothesize that our mixed reality-based system to manage phantom pain will be feasible and well received by a sample of patients with lower limb amputation needing mirror therapy.

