Aim2: Evaluate functional outcomes in a sample of lower limb amputees (n=10), using this mixed reality-based system to manage phantom pain.

Hypothesis 2: Using this system, we hypothesize that patients who participate in our mixed reality-based system will show improvements in patient-reported outcome measures (PROs). We also hypothesize that this mixed reality-based system will help to alleviate the phantom pain based on Pain questionnaires and numerical rating scale (NRS).

Feasibility and Functional Outcomes of a Novel Mixed Reality based system to manage phantom pain for patients with lower limb amputation.

4

3- Study Design

This is a pilot study intended to yield preliminary data that will inform a fully powered trial to determine effectiveness of our novel Mixed Reality based system to manage phantom pain. A HIPAA waiver will be obtained to screen patients with lower limb amputation in the outpatient PM&R clinics. Eligible study candidates will be identified either during an initial visit as an outpatient during clinic visit with the physiatrist, or during review of prior visit with physiatrist. The eligible, pre-screened subjects will undergo a basic evaluation (by rehabilitation physician). After the evaluation, the patient will be asked to participate in the study or sent an invitation letter.

Once an eligible patient consents to enroll in the study with specific emphasis on safely performing the exercises independently at home, the research team will provide the laptop, camera and instruct the patient in its use at their home. The patient will then use the system and perform the personalized home exercises every day for a 1-month period (to evaluate sustainability of exercise behavior). At initial clinic visit, week 1 visit and 1-month visit, the patient will fill out pain questionnaires, functional questionnaire without any identifiable PHI. At the end of this period, the system will be returned by the patient at the final study visit. Research lab staff may retrieve the system may be retrieved from a patient's home if they are unable to bring it to the final visit. The images of the patients performing the exercises will be stored in the encrypted laptop and analyzed at UTD. All videos at UTD will be destroyed after 5 years, but a copy will be kept at the Dallas VA.

4- Functional Outcome Measures:

- a- Numerical rating Scale (NRS)
- b- Brief Pain Inventory (BPI)
- c- McGill Pain Questionnaire
- d- Patient Specific Functional Scale

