- Realistic illusion of phantom limb: As the [name] framework is using RGB-D camera to capture the movement of patients intact limb and mirror it to create the illusion of the phantom limb, the illusion obtained is very realistic instead of using pre-built 3D model of a limb (See Figure 4).
- Patient Encouragement: Use of an immersive gaming environment motivates and keeps the patient engaging while performing exercise. With the help of virtual reality, various engaging game can be developed that helps to remove monotonousness in therapy sessions.
- Feedback with positive Reinforcement: As each game is designed to encourage a patient to perform certain type of exercise, the points earned in the game motivates the patient to perform better.
- Adherence and compliance monitoring: by recording and annotating the therapy sessions, the coaching software will monitor parameters such as number of repetitions, dates and times of exercises, as well as correctness of performing the exercises. This will serve as a real-time diary which is considered more reliable than self-report diaries that rely on patient recall of activity.

Figure 2: Visualization using HMD (Oculus Rift)

Feasibility and Functional Outcomes of a Novel Mixed Reality based system to manage phantom pain for patients with lower limb amputation.

8

[figure not shown]

Figure 3: System Overview

11- Statistical Data Analysis

We will use descriptive methods to characterize our sample population. Pre-post t-tests or equivalent will be used to compare outcomes at one week and 1 month. Given the pilot nature of this proposed study, inferential statistics (and reporting of statistical significance) will not be used.

Feasibility outcomes will be descriptive, including calculating the percent of individuals enrolled in the study versus those eligible and the percent of individuals who remain in the study at month 1.

Aims 1 and 2 will help establish intervention acceptability and feasibility. The images of the patients will be stored in the encrypted laptop and analyzed at UTD. Participants' videos will be destroyed at UTD after 5 years, however, a copy will be kept at the Dallas VA.

12- Reporting Adverse Events

Using weekly telephone support and online ad-hoc support features of the proposed system, we will obtain adverse event data and intervene as needed for any safety issues that may arise during this pilot study.

13- Potential Risks

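### Does Section 11 leave home use and acceptance of the system unmeasured by naming only enrolment and retention as feasibility outcomes?

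*Combined protocol and SAP*

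**What the plan says.** Section 11 (Statistical Data Analysis) deals with feasibility in one sentence: "Feasibility outcomes will be descriptive, including calculating the percent of individuals enrolled in the study versus those eligible", followed by "the percent of individuals who remain in the study at month 1". It then says that "Aims 1 and 2 will help establish intervention acceptability and feasibility", and that the patients' images will be analysed at UTD. For the outcome measures, "Pre-post t-tests or equivalent will be used to compare outcomes at one week and 1 month". The same section rules out inferential statistics and the reporting of significance.

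The data that bear on use and acceptance are described elsewhere:

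- **Session log.** Section 10 (System Overview) says that "the coaching software will monitor parameters such as number of repetitions, dates and times of exercises", along with whether the exercises are done correctly. It adds: "This will serve as a real-time diary which is considered more reliable than self-report diaries".
- **Usability survey.** It is item f in Section 4 and is scheduled in Section 9 at the 1-Month Visit only.
- **Feedback.** Section 4 also gives patients the option of leaving comments and suggestions at the end.

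Two statements give these data a purpose. Hypothesis 1 in Section 2 is that the system "will be feasible and well received by a sample of patients with lower limb amputation needing mirror therapy". Section 3 has the patient "perform the personalized home exercises every day for a 1-month period (to evaluate sustainability of exercise behavior", where the parenthesis closes.

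**The concern.** The two named measures describe recruitment and attendance. Neither counts a session, and neither asks the patient's opinion of the system. Yet Section 3 gives sustained exercise as the reason for the one-month period, and Hypothesis 1 says the system will be well received. The usability survey is the scheduled instrument closest to that second claim. It is collected once, so the pre-post comparison cannot cover it.

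The pilot is meant to inform a fully powered trial. A report confined to enrolment and retention would not tell the designers of that trial whether patients used the system daily or liked it. There is no control group either, so if pain scores did not move, such a report could not separate little use from little effect. With no measure, denominator or patient set named, these could also be chosen after the data are seen.

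**Working it through.** No sample-size calculation applies. The 10 patients in Section 8 are a convenience sample, with no error rate, power or effect size given. The check is arithmetic on planned exposure, then a comparison of the text.

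**1. Planned exposure.** Section 9 gives three games of 5 minutes each: 3 × 5 = 15 minutes, which reproduces the stated daily session length. One session a day for 4 weeks is 7 × 4 = 28 sessions per patient. For 10 patients that is 10 × 28 = 280.

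**2. What retention can show.** Percent remaining = patients still in the study at month 1 ÷ patients enrolled. Suppose all 10 stay, and take three assumed session counts:

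| Sessions done per patient (assumed) | Retention | Sessions done ÷ planned |
|---|---|---|
| 4 | 10/10 = 100% | 4/28 = 14% |
| 14 | 10/10 = 100% | 14/28 = 50% |
| 28 | 10/10 = 100% | 28/28 = 100% |

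Retention contains no usage information beyond what leads a patient to withdraw. This part of the concern is correct.

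**3. The denominator.** Section 9 says 4 weeks and Section 3 says one month. Taking a month as 28 to 31 days, a patient who does 28 sessions scores 28/28 = 100%, 28/30 = 93% or 28/31 = 90%. The spread is at most 10 percentage points. The schedule of events has a four-week diary returned at the 1-Month Visit, so the two terms appear to be used interchangeably. The wording in the two sections should be reconciled, but no stated result depends on it.

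**4. Does the plan limit the report to the two measures?**

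- The feasibility sentence introduces the two percentages with the word *including*. They are examples within a descriptive approach, not a closed list.
- The usability survey is one of the seven listed outcome measures. A survey taken once can only be summarised descriptively, and Section 11 already sets that approach for feasibility.
- Section 10 presents the log as the system's means of monitoring adherence and compliance, by recording and annotating the sessions. Logged dates and times make a session count plausible.
- Sections 3 and 11 both send the session images for analysis, and Section 18 says the laptops are held at UTD for data analysis. No variable is named, but work on the session recordings is clearly intended.

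The harm described therefore needs a restriction that the plan does not contain.

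**5. Standing of the two questions.** Being well received is part of Hypothesis 1, so the survey is the stronger half of the concern. Sustained exercise appears once, in a parenthesis explaining the one-month period. It is not an aim or a hypothesis.

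**6. Weekly reporting.** Assumed weekly counts of 7, 4, 2, 1 and of 3, 4, 3, 4 both total 14 of 28, but in week 4 they give 1/7 = 14% and 4/7 = 57%. A weekly table would show more than a total. That supports a way of presenting the data; it does not show an error in the plan.

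**The case for a change.** The strongest reply is that feasibility is the purpose of this pilot, so its measures should not be left to inference. Section 10 calls the log more reliable than self-report, yet the log appears neither in the Section 4 outcome list nor in Section 11. Under Section 17 the stipend follows the last visit and return of the equipment, with no session count required, so a patient who seldom used the system can still count as retained. Section 8 replaces withdrawn patients whose data are unusable, so adherence could end up reported for completers only. Naming the summaries would take a few words.

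Much of this stands as fact. Retention is a weak proxy for use, no statistic is named for the log or the survey, and counting every patient given the system is sensible practice. What does not follow is that the plan misleads. Choosing a summary after seeing the data matters most where a test or decision rule rests on it, and this plan has neither for feasibility. The remedy's cost is also less certain than it looks. Section 10 lists system features and is not a data-collection section, so whether a completed session can be derived from the log would first have to be checked.

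**Conclusion.** No change to the plan follows. The observation is accurate: Section 11 names enrolment and retention only, and retention can read 100% at any level of use among the 28 planned sessions. But this is missing detail in a descriptive 10-patient pilot. Nothing in the plan bars a summary of the log or the survey, both sources are described, and no sample size, test or decision rule depends on how they are tabulated.

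This conclusion rests on two assumptions. One is that the analysts will read the open list as open, and report the survey and whatever session counts the log supports. The other is that the log does yield a usable count, which the documents make plausible but do not establish. If Section 11 is revised for other reasons, one adherence summary (sessions done out of those planned, for every patient given the system) and one survey summary would make the intention explicit. Medians with ranges, weekly tables and cross-checks against the questionnaires after each game are matters of preference.
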